Previous studies have consistently shown that DENV-4 infections are relatively rare compared to other serotypes. A study in Vietnam found a low number of DENV-4 cases, illustrating the lower incidence of DENV-4 than other serotypes (Ta et al., 2019). A similar study in the Philippines, assessing the efficacy of a tetravalent dengue vaccine candidate (TAK-003) for DENV-4 in eight dengue endemic countries in Asia and Latin America was difficult due to the small number of DENV-4 infection cases, only 7 cases were virologically confirmed (Biswal et al., 2019).

A study on the prevalence and clinical aspects of DENV-1, DENV-2, DENV-3, and DENV-4 in Indonesia showed that DENV-4 was the least common circulating serotype (Harapan et al., 2019). A study conducted in many hospitals examining acute febrile illness in hospitalized patients (AFIRE), found that DENV-4 infection was less common among the cases studied (Utama et al., 2019). Interestingly, DENV-4 is often found in outpatients or during dengue outbreaks. A study in outpatients in West Java found that DENV-4 infection occurred as frequently as other serotypes, but most cases were not clinically typical (Kosasih et al., 2016). In the 2004 Jakarta outbreak, DENV-4 was the second most common serotype after DENV-3 (Suwandono et al., 2006). A study conducted during a dengue outbreak in Jember in 2019, has identified genetic factors associated with DENV-4, suggesting that a combination of selection pressure and changes in genetic mutations may contribute to the dominance of DENV-4 in East Java, Indonesia (Wardhani et al., 2023; Aryati et al., 2020).

One possible explanation for the low prevalence of DENV-4 is that most studies are hospital-based, which may not include untreated mild DENV-4 infections. Besides, NS-1 screening, which is used for detection and identification of DENV-4 cases, has low sensitivity, which further complicates accurate diagnosis (Mata et al., 2020; da Costa et al., 2014). In addition, the sensitivity of NS1 detection varies among secondary infections, with the highest sensitivity of DENV-3 (47.1%), followed by DENV-1 (40.9%), DENV-2 (30%), and DENV-4 (27%) (Kosasih et al., 2013). This is important as secondary

infections of DENV-2, DENV-3, and DENV-4 in Southeast Asia are commonly associated with severe clinical manifestations, indicating the potential for a significant health burden (Soo et al., 2016).

Considering the consequences of undiagnosed dengue infection, the inability to detect DENV-4 using NS1 rapid test may lead to misclassification of cases as non-dengue, resulting in different therapy/ management. This may adversely affect patient therapy, leading to delayed or inappropriate management potentially leading to prolonged illness or worsening of symptoms.

Overcoming the limitations of current diagnostic methods is critical to ensure quick and precise treatment for individuals infected with DENV-4. This is particularly relevant in the context of vaccine development and clinical trials, where accurate serotype identification is essential to evaluate vaccine efficacy and effectiveness. Improving diagnostic capabilities and awareness of the presence and potential impact of DENV-4 infection will contribute to more effective management and control strategies for dengue, ultimately reducing the burden of disease in affected populations. By addressing these issues, healthcare providers and researchers can improve patient prognosis and reduce the challenges posed by DENV-4 infection.

Tangerang, located in Banten province, Indonesia, has a high risk of dengue virus transmission due to its dense population and favorable environmental conditions for mosquito breeding. Despite vector control efforts, dengue remains a significant health challenge in the region. In 2022, as many as 50-100 dengue cases were reported in each public health center and more than 200 patients were hospitalized due to dengue infection.

Focused study in Tangerang, which includes hospitals and public health centers, is essential to obtain local data that can be used as a source of information for interventions that will improve a broader understanding of dengue epidemiology in Indonesia. Tangerang District Hospital is a referral hospital for all public health centers that has several national and multinational clinical studies. Including intervention studies, Tangerang District Hospital has a well-equipped infectious disease laboratory to conduct molecular and serological tests. Collaborating with INA-RESPOND lab, we are also able to conduct Plaque Reduction Neutralization Test (PRNT).

This prospective observational study in Tangerang aims to examine the prevalence, immunologic, virologic, and clinical aspects of dengue virus infection, especially DENV-4. The results of this study will improve our understanding of dengue epidemiology in Tangerang, Indonesia, the relationship between host factors, viral factors, and severity. This study will provide evidence-based information for dengue control, and

contribute to global efforts in developing an effective vaccine for all dengue virus serotypes.

The comprehensive screening efforts of this study will provide important data on other serotypes, enabling a holistic understanding of dengue infection and facilitating inter-serotype characterization. This study will have a significant impact on dengue research, public health policies, and global initiatives to combat this challenging disease.

II. OBJECTIVES

2.1. Primary objective

To determine the clinical characteristics, specific immune responses, and viral serotypes in patients with confirmed dengue virus infection in Tangerang District, Indonesia.

2.2. Secondary objectives

- To assess the prevalence of dengue virus infection among patients with acute fever
- To assess the prevalence of infection with DENV-4 and other serotypes as well as clinical characteristics, immunologic and virologic profiles important for vaccine trials and implementation
- To assess human and viral factors associated with severity of febrile illness due to dengue virus infection
- To increase the capacity of Tangerang District Hospital's Infectious Disease Laboratory/ INA RESPOND Reference Laboratory to perform plaque reduction neutralization test (PRNT).
- To identify other etiologies of fever in Tagerang district

III. CLINICAL HYPOTESIS

Dengue fever is a hyperendemic disease in Tangerang district, Indonesia.

DENV-4 infection is more frequently found at the primary health centers than at the hospital because the clinical symptoms are milder.

Several human and viral factors, such as age, nutrition status, immune status, serotypes, types of infections (primary/secondary) are associated with severity of symptoms.

IV. ETHICAL APPROVAL

This study will be conducted in accordance with ethical guidelines and obtained permission from the relevant institutions and the ethics committee of Tangerang District Hospital.

V. METHOD

5.1. Study design

This study is a prospective observational study that will be conducted in Tangerang Regency, Indonesia. In this study, data will be collected from patients who seek treatment at the Tangerang District Hospital, Kelapa Dua Public Health Center and Bojong Nangka Public Health Center in a one-year period from January 2024 to December 2024. Both public health centers have densely populated areas and have experience in conducting clinical research on COVID-19 vaccination.

Patients suspected of dengue infection will be screened using inclusion and exclusion criteria. Selected participants will be seen at the first visit as clinical data will be collected, routine hematology test and NS-1 RDT will be conducted. Blood specimens will be collected for further testing at Tangerang District Hospital's Infectious Disease Laboratory.

5.2. Inclusion and exclusion criteria

Inclusion criteria:

1. Patients age \geq 4 years old with fever ($\geq 37.5^{\circ}\text{C}$) or history of fever with antipyretic use, lasting less than or equal to 7 days
2. Presence at least one of the following dengue-like symptoms:
 - Headache
 - Retro-orbital pain
 - Nausea/ vomiting
 - Muscle, bone, or joint pain
 - Rash or bleeding manifestations
3. Patient or patient's guardian giving consent to participate in the study

Exclusion criteria:

1. Have a condition that may interfere with study procedures and compliance (based on doctor's assessment)
2. Suspected of focal infection

5.3. Study duration

The study will be conducted over a period of one year, from January 2024 to December 2024. Data will be collected from eligible participants visiting Tangerang District Hospital, Kelapa Dua Public Health Center and Bojong Nangka Public Health Center. Study period will be extended until it reaches the specified number.

5.4. Study procedure

- Recruitment of participants**

Patients who seek treatment at Tangerang District Hospital, Kelapa Dua Public Health Center and Bojong Nangka Public Health Center with dengue-like symptoms will be selected. All those who meet the enrollment criteria will be offered to participate in this study.

- Informed consent**

Potential participants who meet the criteria, or their guardians, will be provided with detailed information about the study. Informed consent will be obtained from potential participants or their guardians prior to participating in the study.

- Data collection**

Data will be collected through structured interviews and medical record review. Information on demographic characteristics, clinical symptoms, medical history, laboratory results, therapy and previous dengue infection will be recorded in the case report form (CRF).

Data on the number of patients presenting with fever to Tangerang District Hospital, Kelapa Dua Public Health Center and Bojong Nangka Public Health Center will be collected for use in identifying the proportion of dengue fever.

- Data management**

Participants will be anonymized to ensure participant confidentiality and the collected data will be stored in a locked cabinet with limited access.

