5.6. Laboratory test

- **Hematology**

Hematology test is conducted at PHCs and Tangerang District Hospital using an automatic hematology analyzer, and the results will be given to the doctor in charge as a basis for diagnosis and therapy.

- **Antigen**

NS1 antigen will be tested at PHCs and Tangerang District Hospital using RDT, and the results will be provided to the doctor in charge as a basis for diagnosis and therapy. The results will be confirmed by NS1 antigen by ELISA.

- **Molecular**

Blood from participants will be subjected to molecular testing. Polymerase Chain Reaction (PCR) to detect and confirm the presence of DENV, and identify dengue serotypes.

- **Serology**

Enzyme-Linked Immunosorbent Assay (ELISA) will be used to detect dengue specific antibodies (IgM and IgG), Rapid Diagnostic Test (RDT) to detect IgM for acute dengue infection, and IgG to determine primary or secondary infection.

- **Plaque Reduction Neutralization Test (PRNT)**

PRNT will also be performed to assess serotype-specific neutralizing antibodies in a subset of specimens (specimens from all severe cases and randomized mild cases as controls).

VI. STATISTICAL ANALYSIS AND SAMPLE SIZE JUSTIFICATION

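### Dengue among acute fever: the planned fever count covers all febrile patients but study testing covers only participants, so their ratio is at best a minimum

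*Combined protocol and SAP*

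**What the plan says.** - **Target.** Section 2.2 lists as a secondary objective "To assess the prevalence of dengue virus infection among patients with acute fever".
- **Denominator source.** Section 5.4 (data collection) has the three sites supply the number of patients presenting with fever, which "will be collected for use in identifying the proportion of dengue fever". No limit of age, fever duration, symptoms or consent is put on that count.
- **Who enters the study.** Section 5.1: "Patients suspected of dengue infection will be screened using inclusion and exclusion criteria". Section 5.2 requires age 4 years or over, fever lasting at most 7 days, and consent, and also "Presence at least one of the following dengue-like symptoms". It excludes suspected focal infection and conditions that would interfere with study procedures.
- **Who is tested.** Section 5.1 gives the NS1 rapid test to selected participants. Section 5.6 says "Blood from participants will be subjected to molecular testing". No study testing of other febrile patients is described.
- **Analysis.** Section 6.2 promises prevalence estimates for DENV1-4 with confidence intervals. It names no numerator or denominator and does not mention febrile patients outside the study.

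**The concern.** The fever count and the case count describe different groups. Cases can come only from people who passed the eligibility filter, consented and were tested. The fever count includes everyone who presented with fever. Dividing one by the other assigns zero dengue to all the rest.

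The documents give no ground for that zero. The group outside the study includes eligible patients who decline, children under 4, patients with fever beyond 7 days and patients with none of the listed symptoms. The background says that mild DENV-4 infection may go unseen in hospital-based studies, and that most DENV-4 cases in one outpatient study were clinically atypical.

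At stake is how the secondary objective is reported. A minimum could be published as the prevalence, with an interval that looks precise because it reflects only the number counted.

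**Working it through.** The plan states no prevalence or precision figure to reproduce. Its only relevant number is the case target in section 6.3: 100 + 100 + 200 = 400 (the sum is mine).

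**Symbols.** All values of f, p and r below are assumptions, because the documents give none.
- f = share of all fever patients tested by the study
- p = proportion with dengue among those tested
- r = dengue risk in those not tested, relative to those tested

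**Step 1: the bias.** Take a case definition without error.
- Ratio (cases / all fever patients) = f·p
- True proportion = f·p + (1 − f)·r·p
- Ratio / truth = f / (f + (1 − f)·r), which does not depend on p

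For f = 0.8 and r = 0.5: 0.8 / (0.8 + 0.2 × 0.5) = 0.8 / 0.9 = 0.889.
For f = 0.5 and r = 0.5: 0.5 / (0.5 + 0.5 × 0.5) = 0.5 / 0.75 = 0.667.

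| f | r = 0 | r = 0.25 | r = 0.5 | r = 1 |
|---|---|---|---|---|
| 0.8 | 1.000 | 0.941 | 0.889 | 0.800 |
| 0.5 | 1.000 | 0.800 | 0.667 | 0.500 |
| 0.3 | 1.000 | 0.632 | 0.462 | 0.300 |

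**Step 2: limits without any assumption on r.** The true proportion lies between f·p and f·p + (1 − f), if there are no false results among the tested. At p = 0.30:
- f = 0.8: 0.8 × 0.30 = 0.24 up to 0.24 + 0.20 = 0.44
- f = 0.5: 0.5 × 0.30 = 0.15 up to 0.15 + 0.50 = 0.65

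**Step 3: does the confidence interval cover the gap?** For C cases, the number of fever patients is F = C / (p·f). With U the upper Wilson 95% limit of C/F (my choice; section 6.2 names no method), the interval excludes the truth once r exceeds r* = (U/p − f) / (1 − f).

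Hospital, C = 200, p = 0.30, f = 0.8: F = 200 / 0.24 = 833; ratio 0.240, interval 0.212 to 0.270 (U = 0.2701); r* = (0.2701/0.30 − 0.8) / 0.2 = 0.50.

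Range of r* for p from 0.5 down to 0.1, at the section 6.3 site targets:

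| Site | f = 0.8 | f = 0.5 |
|---|---|---|
| Each health center (100 cases) | 0.618 to 0.818 | 0.179 to 0.209 |
| Hospital (200 cases) | 0.435 to 0.565 | 0.125 to 0.144 |

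At f = 0.8 a site interval tolerates a fair amount of dengue outside the study. At f = 0.5 it tolerates little.

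**Step 4: when the ratio is not a minimum.** False positives can reverse the direction. With an assumed specificity of 0.95, full sensitivity, p = 0.30 now the share testing positive, f = 0.8 and r = 0, the true proportion in the tested is (0.30 − 0.05) / 0.95 = 0.263. The truth in all fevers is 0.8 × 0.263 = 0.211, against a ratio of 0.240. So the word minimum needs a specific case definition.

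**The case against.** **The ratio is inferred.** No section divides cases by all fever patients, and section 6.2 names no denominator. A proportion among participants, with the fever count as context, would also fit the text. This stands as a limit on certainty. But the only stated use of the fever count is the dengue proportion, and nothing in the plan rules out the biased reading.

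**Not tested by the study is not the same as untested.** The background reports 50-100 dengue cases per health center and over 200 dengue hospitalizations in 2022, so dengue is diagnosed there in routine care. This is fair, but the plan does not collect routine results from non-participants, so they cannot enter the numerator.

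**Stronger readings that a reader might infer:**
- *Large undercounting from NS1.* The background quotes NS1 sensitivity of 27% to 47.1% in secondary infection. That is not a basis here, because section 5.6 also applies PCR and IgM/IgG to participants. No section proposes NS1 alone.
- *The interval almost always misses the truth.* Pooling all 400 cases gives r* of 0.307 to 0.392 at f = 0.8. Estimates by site give the higher values in the table, so the pooled figures overstate the problem at site level.
- *The missing case definition is an equal fault.* Section 2.1 concerns "patients with confirmed dengue virus infection in Tangerang District, Indonesia". Section 5.6 says of the NS1 rapid test "The results will be confirmed by NS1 antigen by ELISA", and says that PCR serves "to detect and confirm the presence of DENV, and identify dengue serotypes". No rule says which results make a case. The tests are named, so this is a missing detail, relevant here because the numerator needs it.

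**Conclusion.** The denominator point holds. If the fever count is used as section 5.4 indicates, each febrile patient not tested by the study counts as dengue-negative, and with a specific case definition and matched dates the ratio is a minimum whose interval leaves those patients out.

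The documents do not support saying that prevalence will be understated by a known amount, or at all. The bias is zero if no patient outside the study has dengue (r = 0) or if everyone is tested (f = 1). The illustrative recoveries of 0.89 and 0.67 rest on assumed f and r and an error-free case definition.

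The point concerns one descriptive secondary objective. The primary objective describes confirmed cases and does not use this ratio. It should be fixed because the target and the planned data do not match and the correction is cheap.

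**What to change.** In sections 5.4 and 6.2:

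1. Estimate prevalence as laboratory-confirmed dengue divided by participants enrolled and tested, by site with 95% confidence intervals. Label it as prevalence among enrolled, dengue-suspected acute febrile patients aged 4 years or over. State one case definition built from the section 5.6 tests and apply it alike at all sites. Section 5.5 takes second specimens from only 25% of health-center participants, so the definition should say how second-visit results count.
2. Report confirmed cases divided by all fever patients only as a minimum proportion. Pair it with (cases + patients not tested by the study) divided by all fever patients, as an upper limit that assumes no false negatives among the tested. Add a short sensitivity table over r.
3. Count fever patients, not visits, over the same dates as enrolment at each site, including any extension under section 5.3.

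The cost is wording and one small table. No new test or study visit is needed, though the sites must be able to identify repeat attendances. The downside is that the main estimate covers a narrower population than section 2.2 names, and the all-fever figure becomes a range that may be wide (24% to 44% or 15% to 65% in the illustration).

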5.5. Clinical data and specimen collection time

- Hospitalized participants**

The data and specimens to be collected are data at the time of the first visit to the hospital and at the second visit. For participants with a positive NS1 RDT result at the first visit, second visit data will be collected when the participant is scheduled to be discharged from hospital inpatient care. For participants with a negative NS1 RDT result at the first visit, data for the second visit will be collected within 7-14 days of the first visit.

- **Participants from Public Health Centers**

Data and specimens to be collected are data and specimens at the time of the visit to the public health centers, while the second data and specimens are only taken as much as 25% of the number of participants of the first visit, with a window period of 7-14 days after the first visit. The determination of participants for the second visit is determined by study's team based on clinical judgment.

- **Clinical evaluation**

Participants will undergo a clinical assessment to evaluate the severity of the disease, including the presence of signs of severe clinical manifestations.

- **Type and amount of specimens to be taken**

- **Serum**

Serum obtained with a 4 mL yellow cap gel separator tube, all serum specimens obtained will be sent to Tangerang District Hospital's Infectious Disease Laboratory/INA-RESPOND lab for viral culture and PRNT.

- **Whole blood dan plasma**

Whole blood specimens in 3 mL purple cap EDTA tubes (adult) or 2 mL purple cap EDTA tubes (pediatric) will be used for hematology test, RDT IgM/IgG, and RDT-NS1 testing, the remaining plasma will be sent to Tangerang District Hospital's Infectious Disease Laboratory for ELISA and PCR testing.

5.6. Laboratory test

- **Hematology**

Hematology test is conducted at PHCs and Tangerang District Hospital using an automatic hematology analyzer, and the results will be given to the doctor in charge as a basis for diagnosis and therapy.

- **Antigen**

NS1 antigen will be tested at PHCs and Tangerang District Hospital using RDT, and the results will be provided to the doctor in charge as a basis for diagnosis and therapy. The results will be confirmed by NS1 antigen by ELISA.

- **Molecular**

Blood from participants will be subjected to molecular testing. Polymerase Chain Reaction (PCR) to detect and confirm the presence of DENV, and identify dengue serotypes.

- **Serology**

Enzyme-Linked Immunosorbent Assay (ELISA) will be used to detect dengue specific antibodies (IgM and IgG), Rapid Diagnostic Test (RDT) to detect IgM for acute dengue infection, and IgG to determine primary or secondary infection.

- **Plaque Reduction Neutralization Test (PRNT)**

PRNT will also be performed to assess serotype-specific neutralizing antibodies in a subset of specimens (specimens from all severe cases and randomized mild cases as controls).

VI. STATISTICAL ANALYSIS AND SAMPLE SIZE JUSTIFICATION

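### PRNT severity comparison: neither the visit nor the fever day is fixed, matched or adjusted for, so a severe-versus-mild titre difference may reflect sampling day, in either direction

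*Combined protocol and SAP*

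**What the plan says.** Section 5.6 limits neutralization testing to part of the specimens: "PRNT will also be performed to assess serotype-specific neutralizing antibodies in a subset of specimens". The part is defined by outcome: "specimens from all severe cases and randomized mild cases as controls". No visit, fever day, matching factor or number of controls is given.

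The comparison this implies serves a secondary objective in 2.2: "To assess human and viral factors associated with severity of febrile illness due to dengue virus infection". Section III also lists immune status and primary or secondary infection among the factors expected to relate to severity.

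Three other places bear on when the serum is drawn and how it is used:

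- **5.2** admits patients with fever "lasting less than or equal to 7 days".
- **5.5** sets the second visit by site and NS1 rapid test result. For NS1-positive inpatients, "second visit data will be collected when the participant is scheduled to be discharged from hospital inpatient care". For NS1-negative inpatients, "data for the second visit will be collected within 7-14 days of the first visit". At the health centres only 25% of participants give a second specimen, at 7 to 14 days, and the study team chooses them on clinical judgment.
- **5.5** also states that "all serum specimens obtained will be sent to Tangerang District Hospital's Infectious Disease Laboratory/INA-RESPOND lab for viral culture and PRNT", which does not fit the subset in 5.6.

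Section 6.2 covers descriptive summaries, serotype prevalence, and comparisons of DENV-4 with the other serotypes. It contains no titre analysis and no mention of fever day. Section 6.1 does not list day of illness as a variable.

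**The concern.** Choosing controls by severity has no evident purpose other than to compare them with the severe cases. If neutralizing titres change over the days when serum is drawn, the comparison is fair only if the two groups are sampled at similar points in the illness. Nothing in the plan secures that. A simple random draw of mild cases carries over whatever fever-day distribution the mild cases happen to have. With the visit left open, specimens from quite different phases of illness could be set against each other.

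This is the plan's only route for studying neutralizing antibody as a possible severity factor. If sampling day differs between the groups, a titre difference could be taken for an immune correlate of severity when it shows only when the blood was taken. A real difference could equally be masked. Adjusting afterwards helps only where cases and controls overlap in fever day, and the draw is the stage at which overlap can be secured.

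**Working it through.** The plan gives no figure for this comparison: no number of severe cases or controls, no effect size and no titre standard deviation. There is nothing to reproduce. The check asks whether sampling day is tied to severity under the plan's own schedule, and then what a given gap would do.

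**Step 1: sampling windows (5.2, 5.5).** First-visit serum falls on fever day 0-7. Second-visit serum on the 7-14 day schedule falls between 0 + 7 = 7 and 7 + 14 = 21 days from fever onset. Discharge serum has no fixed day.

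**Step 2: severe-minus-mild gap in sampling day, by choice of specimen.** From the documents: the 7-14 day window (midpoint 10.5) and the 25% second-visit fraction. Assumed, not in the documents: severe cases are inpatients; mild controls all come from health centres; inpatient stay L = 3 to 7 days; a fraction f = 0.3 to 0.7 of severe cases is NS1-positive; and the first-visit gap g is 0 to 2 days.

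Mean time from first to second visit in severe cases is S = f·L + (1 − f)·10.5. Its lowest value is 0.7·3 + 0.3·10.5 = 5.25 and its highest is 0.3·7 + 0.7·10.5 = 9.45.

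- **First visit only:** gap = g, so 0 to +2 days. This only restates the assumption.
- **Second visit only:** gap = g + S − 10.5. From 0 + 5.25 − 10.5 = −5.25 to 2 + 9.45 − 10.5 = +0.95 days. With g = 0 it is −5.25 to −1.05.
- **Last available specimen:** gap = g + S − 0.25·10.5. From 5.25 − 2.625 = +2.625 to 2 + 9.45 − 2.625 = +8.825 days.
- **Both visits pooled:** gap = g + S/2 − (0.25·10.5)/1.25. From 2.625 − 2.1 = +0.525 to 2 + 4.725 − 2.1 = +4.625 days.

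Even with no first-visit difference (g = 0), the schedule alone makes severe cases earlier on second-visit serum and later on pooled or last-available serum. The sign depends on a choice the plan does not make.

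**Step 3: effect of a gap on the titre ratio.** Assume no true difference and a constant daily fold rise r of 1.25 to 2. The documents give no such rate. False ratio, severe to mild, = r^gap.

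| Gap | r = 1.25 | r = 2 |
|---|---|---|
| +1 day | 1.25 | 2 |
| +2 days | 1.25² = 1.56 | 2² = 4 |
| −1 day | 1/1.25 = 0.80 | 1/2 = 0.50 |
| −2 days | 1/1.5625 = 0.64 | 1/4 = 0.25 |

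These ratios should not be extended to the larger gaps in step 2, because a constant daily rise over that span is a further assumption.

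**The case against.** A reader might infer that severe patients are sampled later in the antibody rise, so that titres in severe cases would be inflated. The documents do not support that. No section gives fever day by severity. Severe signs may appear late in the illness, but first-visit serum is taken at presentation, so a patient who presents early and deteriorates in hospital has an early first specimen. All participants share the same 7-day limit. On second-visit serum, the schedule would often sample NS1-positive inpatients at discharge earlier than health-centre participants at 7 to 14 days, which reverses the bias. An illustration using only a positive lag would assume the disputed sign, so the table gives both.

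It can also be said that 6.2 contains no titre comparison, so the plan makes no inference to be biased. That is correct as to the wording. But the severity objective, the hypothesis in Section III and the term for the mild group all point to a comparison, and its absence from 6.2 means that no safeguard is written either.

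Two further points stand. That titres change materially over the sampling days is an assumption, because the documents do not say so. And adjustment for fever day, with the visit fixed, might be enough if cases and controls overlap well. The plan provides for neither. Fever-day strata would also leave site and primary or secondary infection status unaddressed.

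**Conclusion.** The point holds as a matter of uncontrolled confounding with unknown sign. The PRNT visit and fever day are not fixed, matched or adjusted for, and specimen availability and timing depend on site and NS1 result. A severe-versus-mild titre difference may therefore reflect sampling day in either direction.

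The size cannot be determined from the documents. Under the assumed daily rise, a gap of only 1 day could produce a false ratio of 1.25-2 or 0.5-0.8, and 2 days 1.6-4 or 0.25-0.64. If the groups happen to be sampled on the same fever days, there is no such bias.

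The point does not extend to serotype identification, which 5.6 assigns to PCR. It affects a laboratory subset serving a secondary objective, not the case target or the prevalence estimates. It should still be corrected before specimens are selected, because lack of overlap is hard to repair afterwards.

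**What to change.** In 5.6, for the severity comparison:

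- Use first-visit serum for every severe case and every control.
- Draw mild controls at random within fever-day strata covering days 0-7 (for example 0-3, 4-5 and 6-7), in proportion to the severe cases.
- Report second-visit PRNT separately, as response to infection.

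In 6.2, add the comparison itself: log titre analysed within the fever-day strata, or in a model with fever day as a covariate. In 6.1, add fever day at each specimen as a recorded variable. First-visit fever duration must already be established to apply the 7-day limit in 5.2.

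Reconcile 5.5, which sends all serum for PRNT, with 5.6, which tests a subset. If all serum is tested, the control draw matters less, but the visit and fever day still have to be handled in the analysis.

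Cost: wording and a stratified draw list, using serum already collected. The draw has to wait until severity and fever day are known, and sparse strata may need merging. The plan gives no number of controls, so the effect on assay count cannot be checked, but the change does not itself call for more controls. First-visit serum is still drawn during the illness, so even a well-matched comparison would not measure immunity before infection.
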